3.6.3.3 Adverse Events

The collection periods for AEs are shown in Table 3-3.

Table 3-3 Collection Periods for Adverse Events

Type of Event	Collection Period
Unsolicited adverse events (non-serious)	First 14 days after each vaccination (spontaneous adverse events, if any) Diary review and interview at study visit 14 days after each vaccination.
Solicited adverse events	First 7 days after each vaccination (solicited adverse events recorded daily in diary card) Diary review and interview at study visit 14 days after each vaccination.
Adverse events of special interest	Entire post-vaccination study period (i.e., 421 days).
Serious adverse events including medically important adverse events	Entire post-vaccination study period (i.e., 421 days).

Solicited AEs are events the participant is specifically asked about. These AEs are commonly observed soon after the receipt of vaccination. For this study, solicited AEs to be collected include:

- Injection site reactions
Redness, swelling, tenderness/pain

- Systemic adverse events

Fever, Arthralgia, Myalgia, Fatigue, Headache, Rash, Chills, Nausea

Solicited injection site reactions will be considered causally related to the investigational product.

Adverse events of special interest represent a subset of AEs that include autoimmune diseases and other systemic disorders of interest that could potentially have an immune etiology. AEs of special interest are listed in Appendix A. The PI should use clinical and scientific judgment in deciding whether other AEs (i.e., events not listed in Appendix A) could have an autoimmune origin. The investigator will report AEs of special interest in the eCRF, hereby informing the sponsor's medically responsible persons.

All participants will be provided a diary card, a thermometer to record axillary temperature, a ruler to measure injection site redness and swelling, and instructions on how to use the diary for AE and CM recording, for the first 7 days after each vaccination.

In the period from 8 days after the vaccinations and until the diary card review at 14 days after each vaccination the participants are instructed to fill in the diary only in case they experience an AE or CM intake.

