5.4 Assessing Causal Relationship “Relatedness” of an Adverse Event

For all AEs, the investigator and, for SAEs, also the sponsor’s medically responsible person will determine if there is a **causal relationship** to the investigational product without knowledge of whether active vaccine or placebo was administered. A number of factors will be considered in making this assessment, including: 1) the temporal relationship of the event to the administration of the investigational product 2) whether an alternative etiology has been identified and 3) biological plausibility. Causality of all AEs should be assessed by the investigator using the following question:

“Is there a reasonable possibility that the AE may have been caused by the investigational product?”

- **YES (related):** There is a reasonable possibility that the investigational product contributed to the AE. This includes AEs that are considered possibly, probably or certainly related.
- **NO (not related):** There is no reasonable possibility that the AE is causally related to the administration of the investigational product. There are other, more likely causes and administration of the investigational product is not suspected to have contributed to the AE.

The site PI and sponsor’s medically responsible person will both determine the causality of a SAE and it is expected that communication and consultation may occur in this assessment.

Every effort should be made by the investigator to determine the existence of any pre-existing conditions (e.g., headaches on Study Day 0 with onset prior to study vaccination) which must be taken into consideration when assessing the causal relationship of an AE. Pre-existing conditions should be recorded in the eCRF as baseline history and substantiated by appropriate source documentation. Intermittent conditions such as headaches may not be present on Study Day 0 but may represent an AE if the intensity or duration of the event is worse than usual following administration of the investigational product.

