7.2 Analysis and Presentation of Safety Endpoints

7.2.1 Adverse Events

AEs will be regarded as treatment emergent AEs (TEAEs) if they occur after the 1st vaccination.

The collection periods for AEs are shown in the below table:

Table 3: Collection of AEs

Type of Event	Collection Period
Unsolicited adverse events (non-serious)	First 14 days after each vaccination (spontaneous adverse events, if any) Diary review and interview at study visit 14 days after each vaccination.
Solicited adverse events	First 7 days after each vaccination (solicited adverse events recorded daily in diary card) Diary review and interview at study visit 14 days after each vaccination.
Adverse events of special interest	Entire post-vaccination study period (i.e., 421 days).
Serious adverse events including medically important adverse events	Entire post-vaccination study period (i.e., 421 days).

Solicited adverse events are defined as events occurring within 7 days after a vaccination and of the following types:

- the injection site reactions *redness, swelling, and tenderness/pain*
- the systemic adverse events *fever* (i.e., events with PT *pyrexia* also named temperature reactions), *arthralgia, myalgia, fatigue, headache, rash, chills, and nausea*.

Solicited injection site reactions will be considered related to the IMP regardless of the causality assessment by the investigator. Therefore, related events consist of both solicited events and investigator-defined related events. Related AEs are defined as adverse reactions (ARs).

Presentations of serious adverse events (SAEs) will include medically important AEs.

An overall summary table of treatment emergent AEs by treatment will be made. The overall summary table will include number of events, number of participants, and proportion of participants in the safety analysis set reporting TEAEs (including solicited AEs), solicited AEs, AESIs, Treatment emergent SAEs, Fatal SAEs, related AEs, related SAEs, suspected unexpected SARs (SUSAR), AEs leading to discontinuation of IMP, AEs leading to discontinuation of trial, TEAEs by severity, and TEAEs by outcome. The same will be repeated for AEs occurring within 14 days after vaccination, SAEs, AESIs, solicited AEs and solicited SAEs occurring within the 7 days after each vaccination, and unsolicited AEs and SAEs occurring within the first 14 days after each vaccination.

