Yyy/ xxxxx	xxx	1	Xxxxxxxxxxxxxxxxxx/ XXXXXXXXXXXXXXXX/ XXXXXXXXXXXXXXXX	Ddmmmyyy/ xx Ddmmmyyy		x/xxx .	xxxxx/ xxxxx/ xxx	xxxxx/x	xx.x

Page 1 of x

Trial: POR A-055
 Program: <program_name>.sas - output: <output_name>.rtf - executed: DDMMYYYY

Sponsor: SSI & IAVI
Vaccine: H56:IC31
Trial: POR A-055

Document type:
Listing shells

Status: Final
Version: 2.0
Date: 15 SEP 2023

Listing 16.2.7.4: Unsolicited adverse events within 14 days after vaccination – Safety analysis set

< Layout similar to listing 16.2.7.1 >

Listing 16.2.7.5: Adverse reactions – Safety analysis set

Site/ Participant id	Treatment	AE no.	System organ class/ Preferred term/ Reported term	Start date End date	Duration (days)	Onset relative to 1 st / 2 nd injection (days)	Intensity/ outcome	Action taken/ AESI	SAR/ SUSAR
Yyyy/ xxxxxx	H56:IC31	1	Xxxxxxxxxxxxxxxxxxxx/ XXXXXXXXXXXXXXXX/ XXXXXXXXXXXXXXXX	Ddmmmyyy/ Ddmmmyyy	xx	x/ .	xxxxx/ xxx	xxxxxx/ x	X/ x

Page 1 of x

AESI: Adverse event of special interest, SAR: Serious adverse reaction, SUSAR: Suspected unexpected serious adverse reaction.
Solicited injection site reactions are considered related to the IMP regardless of the causality assessment by the investigator
Trial: POR A-055
Program: <program_name>.sas - output: <output_name>.rtf - executed: DDMMYYYY

Listing 16.2.7.6: Adverse events of special interest – Safety analysis set

< Layout similar to listing 16.2.7.1 >

Listing 16.2.7.7: Serious adverse events – Safety analysis set

< Layout similar to listing 16.2.7.1 >

Listing 16.2.7.8: Adverse events leading to discontinuation of vaccination or withdrawal from trial – Safety analysis set

< Layout similar to listing 16.2.7.1 >

Listing 16.2.7.9: Fatal adverse events – Safety analysis set

< Layout similar to listing 16.2.7.1 >

Listing 16.2.7.10: Injection site reactions and systemic events occurring more than 14 days after vaccination – Safety analysis set

Site/ Participant id	Treatment	AE no.	System organ class/ Preferred term/ Reported term	Start date End date	Duration (days)	Onset relative to 1 st / 2 nd injection	Intensity/ causality/ outcome	Action taken/ Serious	Type/ Max diameter (mm)/Max temp (°C)
Yyyy/ xxxxxx	xxx	1	XXXXXXXXXXXXXXXXXXXX/ XXXXXXXXXXXXXXXXXXXX/ XXXXXXXXXXXXXXXXXXXX	Ddmmmyyyy/ xx Ddmmmyyyy		xx/ x	xxxxx/ xxxxx/ xxx	xxxxxxx/ x	xxxxxxx/ xx/xx.x

Page 1 of x

*Injection site reactions are events marked as Injection site reactions in the eCRF.

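### One sentence in SAP 7.2.1, if programmed literally, would count solicited systemic events judged unrelated as adverse reactions, contrary to the protocol

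*SAP*

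**What the plan says.** SAP 7.2.1 opens the definition this way: "Solicited adverse events are defined as events occurring within 7 days after a vaccination and of the following types". Two groups follow. One is redness, swelling and tenderness/pain at the injection site. The other is systemic: fever together with "arthralgia, myalgia, fatigue, headache, rash, chills, and nausea".

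The section then sets the causality rule in two steps. The first is "Solicited injection site reactions will be considered related to the IMP regardless of the causality assessment by the investigator". The second, offered as its consequence, is "Therefore, related events consist of both solicited events and investigator-defined related events". Related AEs are then equated with adverse reactions.

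The protocol's rule, in 3.6.3.3 and again in 5.13, is "Solicited injection site reactions will be considered causally related to the investigational product". For adverse events in general, protocol 5.4 says: "Causality of all AEs should be assessed by the investigator using the following question". Protocol 5.5 defines an adverse reaction as an AE that has been assessed as related.

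**The concern.** The second step in SAP 7.2.1 uses a term that the section has just defined, and the definition is wider than the premise. On the literal wording, a headache or fever within 7 days of vaccination is an adverse reaction whatever the investigator decided. The protocol gives no such override for systemic events.

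Some solicited systemic events may well be judged unrelated. Participants are still on TB treatment at the first vaccination (inclusion criterion 7), and fever is one of the listed TB symptoms (protocol 3.6.1).

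What is at stake is the related/not related split in the safety tables, and whether those tables agree with the adverse-reaction listing. The SAP also plans outputs for solicited SAEs and a related-SAE row. A serious solicited systemic event could therefore be counted as related against the assessments of both the investigator and the sponsor's medically responsible person, which decide the classification under protocol 5.10.

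**Working it through.** The documents give no adverse-reaction count or rate, so there is no figure to reproduce. The check is a comparison of text, followed by a scale for what a literal reading could do.

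**Step 1: the rules side by side.**

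| Place | What is related without the investigator's judgement |
|---|---|
| Protocol 3.6.3.3 and 5.13 | Solicited injection site reactions only |
| Protocol 5.4 and 5.5 | Nothing further; the investigator assesses causality, and a reaction is an AE assessed as related |
| SAP 7.2.1, sentence before the one at issue | Solicited injection site reactions only |
| SAP 7.2.1, sentence at issue | All solicited events |
| SAP Listing 16.2.7.5, footnote | Solicited injection site reactions only: "Solicited injection site reactions are considered related to the IMP regardless of the causality assessment by the investigator" |
| SAP Tables 14.3.1.1 and 14.3.1.8, shells | No rule stated |
| SAP section 9 | Three deviations from the protocol (per-protocol set, ITT start point, median time); none on causality |

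One sentence stands against all the others. Of the 3 + 8 = 11 solicited terms, it widens the rule to the 8 systemic ones.

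**Step 2: do the outputs settle it?** Table 14.3.1.1 has rows for related AEs and related SAEs. Its footnote repeats the wide definition of solicited events and does not say what related means. Table 14.3.1.8 splits events into related and not related with no note on the override. Table 14.3.2.5 (solicited systemic reactions) uses the layout of Table 14.3.1.1, so under the literal rule its related row would equal its total row by construction. Listing 16.2.7.3 shows the same systemic events with a causality column. A programmer working from 7.2.1 alone has nothing in the table shells to correct the literal reading.

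**Step 3: scale.** Let N be the number in an arm, and s the share of that arm whose only related event would be a solicited systemic event judged not related. The extra participants counted with an adverse reaction are N × s. With the planned N = 450 per arm, and s assumed because the documents do not give it:

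- s = 0%: 450 × 0 = 0
- s = 5%: 450 × 0.05 = 22.5, about 23
- s = 10%: 450 × 0.10 = 45
- s = 20%: 450 × 0.20 = 90

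The extra count cannot be negative. It is zero if the injection-site-only rule is programmed, or if no solicited systemic event is judged unrelated. Participants who already have an injection site reaction or another related event add nothing to the participant count, although their reclassified events would still add to the event count.

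**Step 4: the comparison between arms.** Write p for the correct percentage, and let V and P denote vaccine and placebo. The literal rule changes the difference from p_V − p_P to (p_V − p_P) + (s_V − s_P). If s_V = s_P the difference does not move, and only the ratio shrinks towards 1. If s_V is larger the difference widens; if smaller, it narrows. The sign of s_V − s_P is not in the documents.

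**The case against.** The strongest reply is that the context already limits the sentence. It is drawn as a conclusion from the sentence before it, and that premise concerns injection site reactions alone. The listing footnote and the protocol say the same, and the SAP, which undertakes to list its deviations, lists none here. A changed rule would contradict every other statement on the subject, so a drafting slip is the likelier explanation. This stands, and it is why the point is minor.

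A reader might infer more: that adverse-reaction rates will be overstated in both arms and the vaccine–placebo contrast diluted. The documents do not support that. Overstatement requires literal programming, and also participants in each arm who have unrelated solicited systemic events. Dilution does not follow from Step 4. Protocol 1.4 names fatigue, myalgia and nausea among the commonest related events with this vaccine, so more such events in the vaccine arm, some judged unrelated, could equally widen the difference.

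Nor does relatedness define a key secondary endpoint. Those are solicited AEs, all AEs within 14 days of each vaccination, and SAEs. The protocol presents the tables by relationship as additional summaries. Solicited systemic events are shown by arm in any case, and the investigator's causality remains visible in Listings 16.2.7.1 and 16.2.7.3, so a careful reader could detect and undo a reclassification.

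None of this makes the sentence correct. It is an operative rule for a reported output, and two programmers could follow the SAP and reach different counts.

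**Conclusion.** Wrong as written; minor severity. SAP 7.2.1 contradicts its own premise, protocol 3.6.3.3, 5.4 and 5.13, and the footnote to Listing 16.2.7.5, without a declared deviation. If it is programmed literally, related-AE counts and potentially related-SAE counts in Tables 14.3.1.1 and 14.3.1.8 could only stay the same or rise, and could disagree with the listing.

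The amount cannot be derived. The 0 to 90 participants per arm shown above rests entirely on an assumed share of 0% to 20% and the planned 450 per arm. The effect on the between-arm contrast is undetermined. Sample size, power, alpha, the primary analysis and the key secondary endpoint definitions are untouched. The wording alone is no evidence that the sponsor chose a broader causality rule or that any reported count is inflated.

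**What to change.** In the disputed sentence of SAP 7.2.1, replace the general term for solicited events with *solicited injection site reactions*, leaving the investigator-defined part as it is. Repeat the Listing 16.2.7.5 footnote on Tables 14.3.1.1 and 14.3.1.8, and derive the related flag once so that every table using those layouts and the listing draw on it.

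The cost is a few words and two footnotes, with no new data or analysis. The change is best made before unblinding, so that the rule is not settled with results in view. If the outputs already exist, the clinical trial report should state which rule was programmed.

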5.1.3 Medically Responsible Person

The medically responsible person in the study is a physician from the sponsor. The medically responsible person will review the safety of the product during the study and will assess the causality of the reported SAEs and provide the expectedness of related SAEs. The medically responsible person is like the site PI, blinded in this study.

Each co-sponsor has a medically responsible person who contributes to performing these tasks.

The site PI can, in case of an emergency, unblind a participant's treatment through a restricted access module in the eCRF (see Section 3.4.1).

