5.8 Assessing "Expectedness" of Serious Adverse Reactions

The expectedness of related SAEs i.e. serious adverse reactions, is assessed by the sponsor's medically responsible person only. The expectedness is assessed against the IB. If the outcome of the assessment is that the reaction is unexpected, then the reaction may represent a suspected, unexpected, serious adverse reaction (SUSAR) and the blind should be broken for this specific participant by the [REDACTED] through the restricted access module in the eCRF.

Only, if the participant has received the investigational product (NOT placebo) AND the related SAE (i.e. serious adverse reaction) is unexpected (i.e. unlisted in the IB), the case represents a SUSAR.

Expected related SAEs (i.e. serious adverse reactions) are consistent with the IB for the investigational product.

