5.10 Reporting of Serious Adverse Events

All SAEs are reported by the clinical study site through the eCRF to the sponsor's medically responsible person and to the [REDACTED] for the entire study period. The clinical study site will be provided with the specific reporting procedures before study start.

All AEs will be assessed for seriousness, intensity and causal relationship to the investigational product by the investigator. If serious (SAEs), the sponsor's medically responsible person will give a second assessment on causal relationship. Both assessments will be documented, but the highest degree of causal relationship will determine the ultimate classification of the event as related or unrelated SAE.

For related SAEs i.e. serious adverse reactions, the sponsor's medically responsible person will subsequently assess the expectedness and, if unexpected, report to the [REDACTED] within one business day.

[figure not shown]
The SAE form for the event must be completed by the investigator within one business day of the clinical study site becoming aware of the event. Investigators must not wait to collect additional information to fully document the SAE before notifying the sponsor's medically responsible person and the [REDACTED]

Fatal or life-threatening SAEs that the investigator suspects are related to the investigational product should be telephoned to sponsor's medically responsible person immediately upon the investigator's awareness of the event. If the investigator or sponsor's medically responsible person is required by the protocol or chooses to suspend enrollment s/he shall immediately create a written memorandum for record to the study file.

Fatal or life-threatening SAEs or SUSARs that occur in Tanzania must be telephoned, faxed or e-mailed to TFDA by the investigator within 24 hours of awareness.

Please refer to below flowchart for the reporting of SAEs:

SAE Reporting

[figure not shown]

Expedited Reporting of SUSARs

Cases of SAEs determined to be both related to investigational product and unexpected should be unblinded. Such SAEs in participants who received active vaccine are SUSARs and are subject to expedited reporting, while such cases in participants who received placebo are not subject to expedited reporting.

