A1 / Axxxxx	Xxxxxx	Y	Visit 3 (Day 0)	ddmmmyyyy	xxx	xxx	xxx	xxx
			Visit 6 (Day 70)	ddmmmyyyy	xxx	xxx	xxx	xxx
A1 / Axxxxx	Xxxxxx	Y	Visit 3 (Day 0)	ddmmmyyyy	xxx	xxx	xxx	xxx
			Visit 6 (Day 70)	ddmmmyyyy	xxx	xxx	xxx	xxx

Page 1 of x

Trial: POR A-055

Program: <program>.sas - output: <output>.rtf - executed: DDMMYYYY

Listing 16.2.6.7: Anti-H56 IgG – Immunogenicity cohort

Site/ Participant id	Treatment	Immunogenicity analysis set (Y/N)	Visit	Date	Anti-H56 IgG (EU/mL)
A1 / Axxxxx	Xxxxxx	X	Visit 3	ddmmmyyyy	xxx
			Visit 6	ddmmmyyyy	xxx

Page 1 of x

Trial: POR A-055

Program: <program>.sas - output: <output>.rtf - executed: DDMMYYYY

Listing 16.2.7.1: Adverse events – Safety analysis set

Site/ Participant id	Treatment	AE no.	System organ class/ Preferred term/ Reported term	Start date End date	Duration (days)	Onset relative to 1 st / 2 nd injection	Intensity/ Causality/ Outcome	Action taken/ AESI/Serious
Yyyy/ xxxxxx	Xxx	1	Xxxxxxxxxxxxxxxxxxxxx/ XXXXXXXXXXXXXXXXXX/ XXXXXXXXXXXXXXXXXX	Ddmmmyyyy/ Ddmmmyyyy	xx	xx/ x	xxxxx/ xxxxx/ xxx	xxxxxxxx/x/x

Page 1 of x

Trial: POR A-055

Program: <program_name>.sas - output: <output_name>.rtf - executed: DDMMYYYYY

Listing 16.2.7.2: Solicited injection site reactions within 7 days after vaccination – Safety analysis set

Site/ Participant id	Treatment	AE no.	System organ class/ Preferred term/ Reported term	Start date End date	Duration (days)	Onset relative to 1 st / 2 nd injection	Intensity/ Causality/ Outcome	Action taken/ Serious	Type/ Max diameter (mm)
Yyyy/ xxxxxx	H56:IC31	1	Xxxxxxxxxxxxxxxxxxxxx/ XXXXXXXXXXXXXXXXXX/ XXXXXXXXXXXXXXXXXX	Ddmmmyyyy/ Ddmmmyyyy	xx	xx/ x	xxxxx/ xxxxx/ xxx	xxxxxxxx/ x	xxxxxxxx/ xx

Page 1 of x

Trial: POR A-055

Program: <program_name>.sas - output: <output_name>.rtf - executed: DDMMYYYYY

Listing 16.2.7.3: Solicited systemic reactions within 7 days from vaccination – Safety analysis set

Site/ Participant id	Treatment	AE no.	System organ class/ Preferred term/ Reported term	Start date End date	Duration (days)	Onset relative to 1 st / 2 nd injection (days)	Intensity/ Causality/ Outcome	Action taken/ Serious	Max temp (°C)
Yyy/ xxxxx	xxx	1	Xxxxxxxxxxxxxxxxxx/ XXXXXXXXXXXXXXXX/ XXXXXXXXXXXXXXXX	Ddmmmyyy/ xx Ddmmmyyy		x/xxx .	xxxxx/ xxxxx/ xxx	xxxxx/x	xx.x
		2	Xxxxxxxxxxxxxxxxxx/ XXXXXXXXXXXXXXXX/ XXXXXXXXXXXXXXXX	Ddmmmyyy/ xx Ddmmmyyy		x/xxx .	xxxxx/ xxxxx/ xxx	xxxxx/x	

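### Under SAP 7.2.1 an SAE that only the sponsor judges related can be missing from the related-SAE count, although protocol 5.10 classifies it as related

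*SAP*

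**What the plan says.** **Protocol.** Section 5.10 starts with the investigator's causality assessment. For SAEs it adds that the sponsor's "medically responsible person will give a second assessment on causal relationship". Both are documented, and "the highest degree of causal relationship will determine the ultimate classification of the event as related or unrelated SAE". Section 5.1.3 gives the same role to the sponsor's physician, who "will assess the causality of the reported SAEs and provide the expectedness of related SAEs". Section 5.4 also has both parties determine the causality of an SAE. Section 5.8 then defines a SUSAR: "Only, if the participant has received the investigational product (NOT placebo) AND the related SAE (i.e. serious adverse reaction) is unexpected".

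**SAP.** Section 7.2.1 contains one explicit override of the investigator: "Solicited injection site reactions will be considered related to the IMP regardless of the causality assessment by the investigator". It goes on to say that "related events consist of both solicited events and investigator-defined related events", and names related AEs adverse reactions (ARs). The overall summary, Table 14.3.1.1, has separate rows for related AEs, related SAEs and SUSARs. The adverse event listing shell (Listing 16.2.7.1) has a single column headed "Intensity/ Causality/ Outcome", and the SAE listing (Listing 16.2.7.7) uses the same layout.

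**Declared departures.** The SAP introduction says that deviations from the protocol's analyses are highlighted in section 9. That section has three items: the per-protocol definition, the start point of the ITT analysis, and median time to recurrence. None concerns causality.

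**The concern.** The protocol fixes a final classification for SAEs that rests on two assessments. The SAP's stated rule for related events uses one of them, plus solicited status. The SAP gives no separate definition of a related SAE, so a programmer following section 7.2.1 would derive the Related SAE row from the investigator's field.

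At stake is agreement between the report and the protocol's own classification. A second consequence is that one table could contradict itself. An unexpected SAE in a vaccine recipient, judged related only by the sponsor, is a SUSAR under protocol 5.8 to 5.10. By the SAP's wording it is not a related SAE. The SUSAR row could then show an event that the Related SAE row does not contain.

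The counts are likely to be small. Protocol 1.4 reports no vaccine-related SAEs in the earlier H56:IC31 experience. If that pattern continued, a single discordant case would decide whether the row reads 0 or 1.

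**Working it through.** The plan gives no figure to reproduce here, so the check compares the two rules.

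**Step 1. Rules.**
- Protocol (5.10, with the automatic rule for solicited injection site reactions in 3.6.3.3 and 5.13): related if investigator = yes, OR sponsor = yes, OR the event is a solicited injection site reaction.
- SAP 7.2.1, read literally: related if investigator = yes, OR the event is solicited.

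**Step 2. All combinations for an unsolicited SAE.**

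| Investigator | Sponsor | Protocol 5.10 | SAP 7.2.1 |
|---|---|---|---|
| related | related | related | related |
| related | not related | related | related |
| not related | related | **related** | **not related** |
| not related | not related | not related | not related |

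The rules disagree in one row of four, and there the SAP count is the lower one.

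**Step 3. Solicited events.** Solicited injection site reactions are related under both rules. One mismatch remains, and it runs the other way. A solicited systemic event that neither assessor judged related counts as related under the SAP's literal wording, but not under the protocol. So the sponsor-only mechanism can only lower the related-SAE count, but the net effect of the SAP's wording on all related SAEs is not fixed in sign.

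**Step 4. Link to the SUSAR row.** Under protocol 5.10 the higher assessment makes the SAE related, the sponsor's physician then assesses expectedness, and 5.8 makes an unexpected case in a vaccine recipient a SUSAR. The third row of the table can therefore yield SUSAR = 1 and Related SAE = 0 for the same event.

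**Step 5. Illustrative size.** The documents give neither the number of SAEs, m, nor the share judged related by the sponsor alone, q. Both are assumed here, the SAEs are taken as unsolicited, and events are treated as independent.

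Chance that at least one is missed = 1 − (1 − q)^m; expected number missed = m × q.

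| Assumed m | q = 1% | q = 5% | q = 10% |
|---|---|---|---|
| 10 | 1 − 0.99^10 = 9.6% | 1 − 0.95^10 = 40.1% | 1 − 0.90^10 = 65.1% |
| 40 | 1 − 0.99^40 = 33.1% | 1 − 0.95^40 = 87.1% | 1 − 0.90^40 = 98.5% |

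The expected number missed runs from 10 × 0.01 = 0.1 to 40 × 0.10 = 4. These figures show how the result depends on the assumptions; they do not forecast this trial.

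**The case against.** The best defence is that the SAP sentence was written for another purpose. It follows from the rule on injection site reactions and explains that override; it does not discuss SAEs with two assessments. Protocol 7.4.6, the safety analysis section, asks for summaries by relationship without saying whose, and protocol 5.1.1 gives the site PI responsibility for the causality of each adverse event. Investigator and sponsor are also expected to consult (protocol 5.4), which makes disagreement less likely. All of this is fair, but it does not remove the gap. Section 5.10 is the only place where the documents state a final classification for SAEs, and the SAP neither adopts it nor declares a departure.

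Four stronger readings are tempting, and the documents do not support them:

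- **That related SAEs are in fact undercounted.** This needs at least one SAE judged related by the sponsor and not by the investigator. The documents report none.
- **That the key secondary endpoint is compromised.** That endpoint is all SAEs, whatever their causality. They are tabulated in Tables 14.3.1.13 and 14.3.1.14 and listed in Listing 16.2.7.7. No SAE is lost from it.
- **That such an event certainly disappears from the adverse reaction listing, or that the listings hold only the investigator's view.** SAP 7.2.1 says the AR listing includes SARs and SUSARs, and Listing 16.2.7.5 has a column for them. If those terms carry their protocol meaning, the event belongs there. The causality column does not say whose assessment it holds.
- **That the SUSAR row is an error because the placebo cell must be zero.** The zero follows from the protocol's own definition in 5.8, and the SAP attaches no test to the row. Showing it differently would be a matter of presentation.

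**Conclusion.** The inconsistency is real and undeclared. As written, SAP 7.2.1 would leave an unsolicited SAE judged related only by the sponsor out of the Related SAE row, although protocol 5.10 classifies it as related. The effect is conditional: zero if the two assessors never disagree in that direction, and one for each event where they do. Its size in this trial cannot be derived from the documents.

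The conclusion assumes that the Related SAE row is programmed from the section 7.2.1 definition, the only definition of related that the SAP gives. It concerns a descriptive safety row and that row's consistency with the SUSAR row beside it. The primary efficacy analysis and the total SAE counts are not touched. It should be corrected before the safety outputs are produced.

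**What to change.** In SAP 7.2.1, state that for SAEs related means related according to the investigator OR the sponsor's medically responsible person. Use this definition for the related-SAE, serious adverse reaction and AR outputs, and show the two assessments as separate columns in the SAE listing. If an investigator-only count was intended, section 9 should say so and give the reason.

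The cost is one sentence, one derivation and one extra listing column. Protocol 5.10 already requires both assessments to be documented. It does not say that the sponsor's is held in the clinical database on which the SAP bases its analyses, so a data transfer and reconciliation may be needed. The related-SAE count may rise slightly. The SUSAR row can stay as it is.
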